## 6.2 Participant Registration

A written, signed, informed consent form (ICF) and a Health Insurance Portability and Accountability Act (HIPAA) authorization must be obtained before any study-specific assessments are initiated. A copy of the signed ICF will be given to the subject and a copy will be filed in the medical record. The original will be kept on file with the study records.

All participants consented to the study will be registered in OnCore®, the UCSF Helen Diller Family Comprehensive Cancer Center Clinical Trial Management System (CTMS). The system is password protected and meets HIPAA requirements.

A list of study subjects will be completed, and will include each subject's study number and initials. The investigator must also maintain a separate log of all the subjects screened for participation in the study but who will not participate, the reasons for their exclusion or non-participation, their initials, and the date on which the subject was excluded.

#### 6.3 Schedule of Procedures and Assessments

#### 6.3.1 Pretreatment Period

#### 6.3.1.1 Screening Assessments

- Administrative Procedures
  - Informed consent
- Clinical Assessments
  - Vital signs including blood pressure and heart rate
  - Medical history and demographic information
  - Baseline conditions assessment
  - Concomitant medications
  - o Documentation of disease assessment
  - Performance status
- Laboratory Assessments
  - o Serum creatinine

#### 6.3.2 Treatment Period

#### 6.3.2.1 Study Procedures, Baseline HP C pyruvate MRI

- Pre-Scan
  - Clinical Assessments
    - Vital signs including blood pressure and heart rate

Before vital signs are measured, the subject should be resting for at least 5 minutes (if possible). The same position will be used each time vital signs are measured for a given subject and blood pressure will be measured from the arm contra-lateral to the site of IMP administration whenever possible.

• Standard MR Scan

Patient is transferred to the MRI suite. Standard 1H MRI exam will be obtained in the abdomen, including T2 weighted imaging, and T1 weighted imaging pre and dynamically following gadolinium contrast administration (gadobutrol at 0.1ml/Kg body weight). If the patient has estimated glomerular filtration rate (eGFR) < 30, gadobutrol will not be administered.

- HP C MR Imaging
  - Study Tx / Drug Admin: Hyperpolarized 13C pyruvate injection

Hyperpolarized 13C pyruvate will be injected intravenously at a dose of 0.43 mL/kg and at a rate of 5 mL/second followed by a 20 mL saline flush at 5 mL/second. The volume to be injected is based upon body weight and is outlined in Appendix 2.

- Imaging Procedures: Dynamic 13C MR imaging
  - 1-2 minutes post-injection
  - 13C 3D MRI sequence with Multiband spectral-spatial excitation pulse for minimal [1-13C] pyruvate saturation and echo-planar imaging (EPI) readout for accelerated spectral-spatial sampling.
  - An optional second HP 13C pyruvate injection and MRI acquisition will be performed within 15 to 60 minutes following completion of the first scan. This repeat injection and scan is optional. This second injection will only occur if there is no adverse reaction to the first injection. The optional second injection and MRI scan are used to assess the repeatability of tumor HP 13C pyruvate metabolism.

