#### Safety Information

Earlier studies of nonhyperpolarized pyruvate outside of the United States were summarized in section 1.2.1

Reported IMP-related AEs in previous studies in humans include:

Cardiovascular: dizziness, catheter site hematoma, heart rate increased, hypertension

Constitutional symptoms: hypoesthesia, unresponsive to stimuli, feeling hot/flushing, fatigue, feeling abnormal

Gastrointestinal: dysgeusia, dry mouth

Genitourinary: micturition urgency

Pain: catheter site pain

Pulmonary: pharyngolaryngeal pain

Neurologic: headache (migraine), parosmia

However, the quality of these prior studies was unclear. The findings from the phase I study of prostate cancer patients at UCSF, which included comprehensive safety monitoring, are summarized in the Background Section.

The dosage of IMP that will be used in this study, and the injection rate of 5 ml/second, have been shown to be safe and well tolerated in the phase I study completed at UCSF. Safety

monitoring included continuous lead 2 EKG monitoring for 10 minutes after injection, monitoring of vital signs, injection site, EKG, and adverse events, and laboratories for two hours after injection. Patients were also evaluated clinically 24 hours and 7 days after injection. No safety concerns were observed.

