## 6.1 Study Calendar

Period / Procedure	Screening	Baseline HP  C pyruvate MRI		Follow up HP  C pyruvate MRI  4w ± 2w post tx initiation			Follow-Up	
		Pre- scan	HP  C MR Imaging	Post-scan	Pre- scan	HP  C MR Imaging	Post- scan	2-3mo interval tx
Study Day / Visit Day	-28d - 0d							initiation
Study Tx / Drug Admin								
HP  C pyruvate injection			Х			X 		
Administrative Procedures								
Informed consent	Х							
Clinical Assessments								
Baseline conditions	Х							
Concomitant medications	Х							
Medical history/Demographics	Х							
Performance status	Х							
Vital signs	Х	Х		X 	X 		X 	
AE assessment				X 			X 	
Laboratory Assessment								
Serum creatinine	Х							
Imaging Procedures								
MR Scan			Х			X 		
Disease Assessment on SOC CT								X 

Vital signs will be collected at the end of the visit (once the final scan is completed). AEs will be assessed following each scan.

<sup>1 Cohort B only: For patients in Cohort B, a follow up HP 13C pyruvate MRI will be obtained as per above procedures at 4 weeks (+/- 2 weeks) following the initiation of systemic therapy or radiotherapy as per clinical care.

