#### Post-Scan

- Clinical Assessments
  - Vital signs including blood pressure and heart rate at the end of the visit (when the last scan is complete).

Before vital signs are measured, the subject should be resting for at least 5 minutes (if possible). The same position will be used each time vital signs are measured for a given subject and blood pressure will be measured from the arm contra-lateral to the site of IMP administration whenever possible.

If the subject experiences an adverse event such as increased heart rate or decreased blood pressure that are deemed clinically significant by the monitoring MD or nurse on site, the subject will be monitored closely until all vital signs are stable.

Therefore, the period for adverse event monitoring will be up to 24 hours. Notably, no significant adverse events have been observed in any of the other ongoing hyperpolarized 13C pyruvate MRI studies.

 AE assessment: For all subjects, a MD or nurse will follow up with the subject with a phone call within 24 hours to assess for any side effects. AEs will also be assessed at the visit, after each scan is completed.

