#### 6.4 Supportive Care

Subjects should receive full supportive care as medically indicated.

The Principal Investigator or designee will be present during the administration and monitoring period.

Any events occurring during or subsequent to the administration of IMP will be addressed as required by the monitoring nurse and/or physician as deemed appropriate.

Additional toxicities that arise, including the determination that the injection administered was not sterile, will be treated at the discretion of the treating physician.

A site-specific, radiology tackle-box will be present at the imaging site. This tackle-box contains at a minimum: epinephrine 1mg/1ml, diphenhydramine 50 mg/ml, glucose tablets, NaCl 0.9% 500 ml bag, atropine 1mg/ml, methylprednisolone 125mg/2ml vial, phentolamine 5 mg vial, albuterol 5.5 gram inhaler, sterile water 10ml vial. Any patient who becomes unstable will be stabilized and transferred to the hospital by ambulance.

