### 7.3 Definitions of Adverse Events

#### 7.3.1 Adverse Event

An adverse event (also known as an adverse experience) is defined as any untoward medical occurrence associated with the use of a drug in humans, whether or not considered drug related. More specifically, an adverse event can be any unfavorable and unintended sign (e.g., an abnormal laboratory finding), symptom, or disease temporally associated with the use of a drug, without any judgment about causality. An adverse event can arise from any use of the drug (e.g., off-label use, use in combination with another drug) and from any route of administration, formulation, or dose, including an overdose.

Laboratory test value abnormalities will not be recorded as AEs unless they are designated as clinically significant, defined as any one of the following: symptomatic, requiring treatment, resulting in dose modification or delay or premature study withdrawal, or placing the subject at risk for other toxicity in the judgment of the treating investigator.

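### Dose 2 is barred after an adverse reaction to dose 1, but no blood pressure or heart rate reading is required between the doses (low-cost improvement, lowest tier)

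*Combined protocol and SAP*

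**What the plan says.** The optional second injection has the same condition at the baseline visit (Section 6.3.2.1) and at the Cohort B follow-up visit (Section 6.3.2.2): "This second injection will only occur if there is no adverse reaction to the first injection". It is given 15 to 60 minutes after the first scan ends, and its stated purpose is to assess repeatability.

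Footnote 2 of the study calendar (Section 6.1) sets the timing of the safety checks: "Vital signs will be collected at the end of the visit (once the final scan is completed). AEs will be assessed following each scan". The post-scan text at both visits agrees with it. Blood pressure and heart rate are also taken before scanning.

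The same post-scan text gives examples of adverse events that call for close monitoring: "increased heart rate or decreased blood pressure that are deemed clinically significant by the monitoring MD or nurse on site". Section 7.3.1 counts signs as well as symptoms: "an adverse event can be any unfavorable and unintended sign (e.g., an abnormal laboratory finding), symptom, or disease". Section 7.3.2 defines an adverse reaction more narrowly, as an adverse event that the drug caused.

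On staffing, Section 6.4 states: "The Principal Investigator or designee will be present during the administration and monitoring period".

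**The concern.** The condition on dose 2 turns on whether dose 1 caused a reaction. The protocol's own examples of adverse events at this visit are changes in heart rate and blood pressure, which can occur without symptoms and are then visible only if measured. The measurement is scheduled after the decision it could inform. This is a stated timing that appears in the calendar and in both post-scan sections, so it is not a detail left out.

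Two things are at stake, both modest. First, a patient with a symptom-free but clinically significant change could receive a second research dose that the protocol means to withhold. Second, in a two-dose session the single post-dose reading follows both injections, so a change cannot be assigned to either one.

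Haemodynamic effects are not foreign to this product. Section 4.1.1 lists among product-related events in earlier human studies: "dizziness, catheter site hematoma, heart rate increased, hypertension". No dose or symptom status is given there, and the section adds that the quality of those studies was unclear.

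**Working it through.** The plan gives no figure to reproduce on this point. The check is a count of required assessments, followed by a comparison of sections.

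**Required checks in a two-dose session** (Sections 6.1, 6.3.2.1, 6.3.2.2)

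| Time | Blood pressure and heart rate | AE assessment |
|---|---|---|
| Before scanning | 1 | none listed |
| After scan 1, before dose 2 | 0 | 1 |
| After the final scan | 1 | 1 |

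Readings: 1 + 0 + 1 = 2, the same as in a one-dose session. Supportive care (6.4), the adverse event sections (7.2 to 7.6) and the monitoring plan (Appendix 4) add no required reading between doses. The instruction to monitor until vital signs are stable applies only after a clinically significant event has been recognised.

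**Sessions affected**

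- Section 8.3.3 scenario, 20 subjects each repeating once: 20 × 1 = 20.
- Every planned patient repeating at every session: Cohort A 20 × 1, plus Cohort B 20 × 2, = 60.
- Sections 3.3 and 8.1.2 allow patients to be replaced or added. Some of those replaced may already have had a two-dose session, so 60 is the ceiling for the 40 planned patients only.
- The repeat is optional, so the number could also fall below 20.

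**Does the phase I experience cover the interval?** Section 4.1.1 says that the phase I safety monitoring included "monitoring of vital signs, injection site, EKG, and adverse events, and laboratories for two hours after injection". Here the 13C acquisition is listed at 1 to 2 minutes after injection, and dose 2 follows scan 1 by 15 to 60 minutes. Dose 2 therefore falls inside the two-hour period over which phase I took vital signs, and no reading is required before it.

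**Would a reading have caught the one recorded hypotension?** The phase I table lists one grade 1 hypotension among 19 patients at 0.43 mL/kg (1/19 = 5%). Section 1.1.1 says that it occurred a day after injection and was thought unlikely to be related. A reading between doses would not have found it.

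**Does a reading fit the interval?** Section 6.3.2.1 asks for 5 minutes of rest before vital signs, if possible. That is 5/15 = 33% of the shortest gap and 5/60 = 8% of the longest.

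The documents give no rate of symptom-free haemodynamic reactions, so no number of missed events is estimated.

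**The case against.** The strongest reply is that the plan made a choice and that the choice is defensible. Adverse events are assessed after each scan, a physician or nurse monitors on site, and the principal investigator or a designee is present. Staff may take a reading whenever they see reason to. The background is reassuring: a repeat volunteer cohort tolerated 0.43 mL/kg well, elderly volunteers showed no notable vital-sign changes (Section 1.1), phase I monitoring raised no safety concerns (1.1.1), and over 20 two-injection human studies noted no adverse effects (1.2). The haemodynamic event described in Section 1.1 occurred at 0.57 mL/kg and came with flushing, which an AE check could detect. All of this stands, and it keeps the point at the lowest tier. It does not show that a symptom-free change would be seen before dose 2. Section 1.2 does not say whether vital signs were taken between injections.

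Three narrower objections also stand. The condition is an adverse reaction, not any adverse event, so a symptom-free change matters only if it is judged clinically significant and drug-caused. Attribution to one dose has no stated analytic use: Section 7.2 analyses patients who received at least one dose, and the stopping rule in 5.1 counts patients. And because vital signs must be taken in the same position each time, an extra reading could mean moving the patient before the repeatability scan.

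A reader might go further and infer that the condition on dose 2 is not checked at all. The required AE assessment after scan 1 rules that out. A reader might also add the doses (2 × 0.43 = 0.86 mL/kg) and infer a haemodynamic risk from the Appendix 3 warning about doses above 0.43 mL/kg. The documents do not support that step. Each injection is at the stated limit and not above it, two separated doses are not one larger bolus, and Section 1.2 cites the short half-life of pyruvate metabolism.

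**Conclusion.** The point holds as a low-cost safety improvement, not as a flaw in the design. Between the two doses the plan requires one AE assessment with no specified measurement and no blood pressure or heart rate reading. A symptom-free, clinically significant change could therefore be missed before an optional research dose. This affects about 20 sessions in the Section 8.3.3 scenario and up to 60 for the 40 planned patients, slightly more with replacements.

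Confidence is high on the schedule itself, which is explicit at both visits. It is much lower on how often the reading would change a decision: the documents give no rate and do not place such an event at 0.43 mL/kg. The risk is probably low. No endpoint uses vital signs, and sample size, power and significance level are untouched.

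**What to change.** In Sections 6.3.2.1 and 6.3.2.2 and in footnote 2 of the study calendar, for two-dose sessions only:

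- Add one blood pressure and heart rate reading after the first 13C scan and before dose 2.
- Take it without moving the patient from the scan position where possible, and take the pre-scan reading in that same position so that the two can be compared.
- Withhold dose 2 if the monitoring physician or nurse judges the change clinically significant. This is the standard already used in the post-scan text.
- Keep the end-of-visit reading and the existing no-adverse-reaction condition, and record the new reading on the case report form.

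The cost is one reading per two-dose session (three readings instead of two), one form line and wording in three places, with no added visits or patients. If the reading cannot be taken in place, repositioning could add variability to the repeat scan and so to the intraclass correlation in Section 8.3.3. An occasional optional repeat may be lost, which makes the 20 repeats assumed there slightly harder to reach. Withholding remains a clinical judgment, because the change sets no numerical threshold.

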#### Post-Scan

- Clinical Assessments
  - Vital signs including blood pressure and heart rate at the end of the visit (when the last scan is complete).

Before vital signs are measured, the subject should be resting for at least 5 minutes (if possible). The same position will be used each time vital signs are measured for a given subject and blood pressure will be measured from the arm contra-lateral to the site of IMP administration whenever possible.

If the subject experiences an adverse event such as increased heart rate or decreased blood pressure that are deemed clinically significant by the monitoring MD or nurse on site, the subject will be monitored closely until all vital signs are stable.

Therefore, the period for adverse event monitoring will be up to 24 hours. Notably, no significant adverse events have been observed in any of the other ongoing hyperpolarized 13C pyruvate MRI studies.

 AE assessment: For all subjects, a MD or nurse will follow up with the subject with a phone call within 24 hours to assess for any side effects. AEs will also be assessed at the visit, after each scan is completed.

## 6.3.2.2 Study Procedures, Follow-Up HP C pyruvate MRI (cohort B only)

For patients in Cohort B, a follow up HP 13C pyruvate MRI will be obtained as per above procedures at 4 weeks (+/- 2 weeks) following the initiation of systemic therapy or radiotherapy as per clinical care.

- Pre-Scan
  - o Clinical Assessments
    - Vital signs including blood pressure and heart rate

Before vital signs are measured, the subject should be resting for at least 5 minutes (if possible). The same position will be used each time vital signs are measured for a given subject and blood pressure will be measured from the arm contra-lateral to the site of IMP administration whenever possible.

Standard MR Scan

Patient is transferred to the MRI suite. Standard 1H MRI exam will be obtained in the abdomen, including T2 weighted imaging, and T1 weighted imaging pre and dynamically following gadolinium contrast administration (gadobutrol at 0.1ml/Kg body weight). If the patient has estimated glomerular filtration rate (eGFR) < 30, gadobutrol will not be administered.

- HP C MR Imaging
  - o Study Tx / Drug Admin: Hyperpolarized 13C pyruvate injection

Hyperpolarized 13C pyruvate will be injected intravenously at a dose of 0.43 mL/kg and at a rate of 5 mL/second followed by a 20 mL saline flush at 5 mL/second. The volume to be injected is based upon body weight and is outlined in Appendix 2.

- Imaging Procedures: Dynamic 13C MR imaging
  - 1-2 minutes post-injection
  - 13C 3D MRI sequence with Multiband spectral-spatial excitation pulse for minimal [1-13C] pyruvate saturation and echo-planar imaging (EPI) readout for accelerated spectral-spatial sampling.
  - An optional second HP 13C pyruvate injection and MRI acquisition will be performed within 15 to 60 minutes following completion of the first scan. This repeat injection and scan is optional. This second injection will only occur if there is no adverse reaction to the first injection. The optional second injection and MRI scan are used to assess the repeatability of tumor HP 13C pyruvate metabolism.

#### Post-Scan

- Clinical Assessments
  - Vital signs including blood pressure and heart rate at the end of the visit (when the last scan is complete).

Before vital signs are measured, the subject should be resting for at least 5 minutes (if possible). The same position will be used each time vital signs are measured for a given subject and blood pressure will be measured from the arm contra-lateral to the site of IMP administration whenever possible.

If the subject experiences an adverse event such as increased heart rate or decreased blood pressure that are deemed clinically significant by the monitoring MD or nurse on site, the subject will be monitored closely until all vital signs are stable.

Therefore, the period for adverse event monitoring will be up to 24 hours. Notably, no significant adverse events have been observed in any of the other ongoing hyperpolarized 13C pyruvate MRI studies.

 AE assessment: For all subjects, a MD or nurse will follow up with the subject with a phone call within 24 hours to assess for any side effects. AEs will also be assessed at the visit, after each scan is completed.

#### **Reporting of MR Findings:**

The HP 13C pyruvate MRI is considered a research test and as such, will not be used in the clinical management of patients enrolled on the study. If there are any clinically relevant abnormal findings detected on standard anatomic MR imaging, these results will be communicated to patient and treating health care provider within 24 hours of completion of MR scan.

#### 6.4 Supportive Care

Subjects should receive full supportive care as medically indicated.

The Principal Investigator or designee will be present during the administration and monitoring period.

Any events occurring during or subsequent to the administration of IMP will be addressed as required by the monitoring nurse and/or physician as deemed appropriate.

Additional toxicities that arise, including the determination that the injection administered was not sterile, will be treated at the discretion of the treating physician.

A site-specific, radiology tackle-box will be present at the imaging site. This tackle-box contains at a minimum: epinephrine 1mg/1ml, diphenhydramine 50 mg/ml, glucose tablets, NaCl 0.9% 500 ml bag, atropine 1mg/ml, methylprednisolone 125mg/2ml vial, phentolamine 5 mg vial, albuterol 5.5 gram inhaler, sterile water 10ml vial. Any patient who becomes unstable will be stabilized and transferred to the hospital by ambulance.

## 7 Reporting and Documentation of Results

#### 7.1 Evaluation of Efficacy (or Activity)

This is a pilot study to investigate whether Hyperpolarized C-pyruvate MRI can provide metabolic information and tumor response assessment in patients with pancreatic ductal adenocarcinoma.

